#### **5.4.4. Management of Dose-Limiting Toxicities or Other Urgent Situations**

In all cases, investigators may employ any measures or concomitant medications, after discussion with the sponsor (whenever possible), necessary to optimally treat the subject.

#### **5.4.5. Follow-Up of Dose-Limiting Toxicities**

Any DLT should be followed until it resolves to baseline or appears to have stabilized for a minimum of 2 weeks. During follow-up, subjects should be seen as often as medically indicated to assure safety.

#### **5.4.6. Procedures for Cohort Review and Dose Escalation**

Telephone conferences will be scheduled by the sponsor with study investigators in order to review cohort-specific data and overall safety data, to agree on dose escalation, adjudicate individual high-grade AEs as potentially dose-limiting, and guide other major study decisions.

#### **5.4.7. Criteria and Procedures for Dose Interruptions and Adjustments of INCB059872**

Study treatment may be delayed up to 2 weeks (14 days) to allow for resolution of toxicity with the exception of irAEs in subjects enrolled in TG E/E1 (see [Table 6](#) for the management of irAEs). Subjects may resume treatment if no medical condition or other circumstance exists that, in the opinion of the investigator, would make the subject unsuitable for further participation in the study. The treating investigator should contact the sponsor to discuss the case of any subject whose treatment has been delayed for more than 14 days before restarting study treatment.

Because subjects may enter the study with extensive pretreatment and/or severe bone marrow infiltration by the primary disease, these dose reduction rules are provided as guidelines (see [Table 5](#)). Individual decisions regarding dose reduction should be made using clinical judgment and in consultation with the sponsor's medical monitor, taking into account relatedness of the AE to the study drug and the subject's underlying condition. Adverse events that have a clear alternative explanation or transient ( $\leq 72$  hours) abnormal laboratory values without associated clinically significant signs or symptoms may be exempt from dose-reduction rules.

**Table 5: Guidelines for Interruption and Restarting of Study Drug**

Chemistry			
Adverse Event		Action Taken	

 
AST and/or ALT is <math>> 3.0 \times</math> ULN and <math>< 5.0 \times</math> ULN; repeat in 1 week and if persistent or increasing or
 
AST and/or ALT is <math>> 5.0</math> AND <math>< 20 \times</math> ULN
 
 
Note: In subjects with liver metastasis-related elevations as baseline, contact sponsor to discuss clinical management and possible dose reductions.
		
 
Interrupt study drug up to 2 weeks (14 days) until the toxicity has resolved to <math>\leq</math> Grade 1 except by approval of the medical monitor.
 
Restart study drug at same dose and monitor as clinically indicated. If rechallenge is positive with AST and/or ALT elevation <math>> 3.0 \times</math> ULN, restart study drug at next lower dose (or at 25% reduction, rounded down to the nearest pill strength); monitor as clinically indicated.
 
	

 
AST and/or ALT is <math>> 20 \times</math> ULN
 
ALT <math>> 3.0 \times</math> ULN, alkaline phosphatase <math>< 2 \times</math> ULN, and bilirubin <math>\geq 2.0 \times</math> ULN (Hy's Law) and no other immediately apparent possible cause of aminotransferase elevation and hyperbilirubinemia, including, but not limited to, viral hepatitis, pre-existing chronic or acute liver disease, or the administration of other drug(s) known to be hepatotoxic.
 
		Discontinue treatment. Discontinue treatment.	
Hematology			
Parameter	Tumor Types	Adverse Event	Action Taken
Platelets ( $\times 10^9/L$ )	Solid tumors	$\geq 25$ to $< 50$	
 
If symptomatic (eg, clinically significant bleeding), discontinue.
 
If asymptomatic, hold until resolved to <math>\geq 75</math> and restart study drug at next lower dose and monitor.
 

		$< 25$	
 
If symptomatic (eg, clinically significant bleeding), discontinue.
 
If asymptomatic, hold until resolved to <math>\geq 75</math>, then restart study drug at next lower dose and monitor.
 

	AML/MDS/MF	N/A	
 
Thrombocytopenia should be managed per institutional standard, relevant to the underlying disease, including initiating or increasing the frequency of platelet transfusion. If there is a suspected causal relationship to INCB059872 in the setting of a decreasing platelet count, hold INCB059872 and/or reduce INCB059872 dose for any of the following: 
 
Platelet decreased <math>> 50\%</math> compared with baseline and below <math>25 \times 10^9/L</math>.
 
Accompanied by any sign of bleeding.
 
Platelet transfusion refractory.
 
 
 
Discontinue if clinically significant bleeding suspected to be related to study treatment.
 
Discuss with medical monitor for dose modifications under any other situations not discussed above, if needed.
 

**Table 5: Guidelines for Interruption and Restarting of Study Drug (Continued)**

Hematology (Continued)			
Parameter	Tumor Types	Adverse Event	Action Taken
Absolute neutrophil count ( $\times 10^9/L$ )	Solid tumors	$\geq 0.5$ to $< 1.0$	
 
1. Interrupt study drug up to 2 weeks (14 days) until the toxicity has resolved to <math>\geq 1.0</math> except by approval of the medical monitor. Granulocyte colony-stimulating factor is allowed in the management of neutropenia
 
2. Restart study drug at next lower dose and monitor.
 

		$< 0.5$	
 
1. If symptomatic (eg, infection), discontinue
 
2. If asymptomatic, interrupt study drug up to 2 weeks (14 days) until the toxicity has resolved to <math>\geq 1.0</math> except by approval of the medical monitor. Granulocyte colony-stimulating factor is allowed in the management of neutropenia. Restart study drug at the next lower dose and monitor.
 

	AML/MDS/MF	N/A	Neutropenia should be managed per institutional standard, relevant to the underlying disease. If there is a suspected causal relationship to INCB059872 in the setting of a decreasing neutrophil count, hold INCB059872 and discuss with the medical monitor.
Hemoglobin (g/dL)	All tumors	$< 6.5$	
 
1. Hold until resolved to <math>\geq 8.0</math>, restart at next lower dose, and monitor.
 
2. If recovery to <math>\geq 8.0</math> does not occur within 14 days of dose interruption or is refractory to transfusion support, discontinue study drug treatment(s) and follow-up per Protocol.
 

Leukocytosis	AML/MDS	N/A	Leukocytosis due to progression of underlying disease should be managed per institutional standard.
Other toxicities			

 
• Any Grade 3 toxicity, if clinically significant and not manageable by supportive care.
 
			
 
1. Interrupt study drug up to 2 weeks (14 days), until toxicity resolves to <math>\leq</math> Grade 1.
 
2. Restart study drug at the next lower dose and monitor as clinically indicated.
 

 
• Any recurrent toxicity after 2 dose reductions.
 
			Discontinue study drug administration and follow-up per Protocol. (Exceptions require approval of sponsor.)

 
• Any Grade 4 toxicity.
 
			Discontinue study drug administration and follow-up per Protocol.

#### 5.4.8. Management of Immune-Related Adverse Events

Nivolumab is considered an immune modulator, and it is possible that irAEs (both nonserious and serious) may occur. Adverse events of a potential immunologic etiology or irAEs may be defined as an AE consistent with an immune phenomenon associated with drug exposure *after all other etiologies have been eliminated*. Immune-related AEs may be expected based on the nature of the study treatment, their mechanism of action, and reported experience with these and other immunotherapies. Special attention should be paid to AEs that may be suggestive of potential irAEs. An irAE can occur shortly after the first dose or several months after the last dose of treatment. Suspected irAEs should be discussed with the medical monitor when possible.

Subjects should receive appropriate supportive care measures as deemed necessary by the treating investigator. Suggested supportive care measures for the management of drug-related AEs with potential immunologic etiology are outlined in [Table 6](#). Detailed supportive care guidelines for specific irAEs can be found in [Appendix H](#). Nivolumab may have specific irAE management guidelines within the package insert; the treating investigator may use labeled guidance or institutional guidelines for the management of irAEs if preferred. For each AE, attempts should be made to rule out other causes, including but not limited to metastatic disease or bacterial or viral infection, which might require specific supportive care.

**Table 6: General Approach to Handling Immune-Related Adverse Events**

irAE	Withhold/Discontinue Nivolumab and INCB059872	Guidance for Restarting Study Treatment	Supportive Care
Grade 1	No action.	Not applicable.	Provide symptomatic treatment.
Grade 2	Withhold nivolumab. May withhold INCB059872 per investigator's discretion. Discontinue if unable to reduce corticosteroid dose to < 10 mg/day of prednisone or equivalent within 6 weeks of toxicity.	May return to treatment if improves to Grade 1 or resolves within 6 weeks. If AE resolves within 4 weeks, subject may restart at the same dose and schedule for both nivolumab and INCB059872. For an AE that does not resolve within 4 weeks, nivolumab should be reduced 1 dose level but INCB059872 may be restarted at the same dose and schedule. If AE does not resolve within 6 weeks, study treatment with both study drugs should be discontinued or discussed with medical monitor.	Consider systemic corticosteroids in addition to appropriate symptomatic treatment.
Grades 3	Withhold or discontinue nivolumab and INCB059872. Discontinue if unable to reduce corticosteroid dose to < 10 mg/day of prednisone or equivalent within 6 weeks of toxicity.	Any restart of study treatment must be discussed with medical monitor before restarting treatment.	Systemic corticosteroids are indicated in addition to appropriate symptomatic treatment. May use 1 to 2 mg/kg of prednisone or equivalent per day. Steroid taper should be considered once symptoms improve to $\leq$ Grade 1 and tapered over at least 4 weeks in most cases.
Grade 4	Discontinue nivolumab and INCB059872.	Not applicable. Any exceptions require medical monitor approval.	Systemic corticosteroids are indicated in addition to appropriate symptomatic treatment. May use 1 to 2 mg/kg prednisone or equivalent per day. Steroid taper should be considered once symptoms improve to $\leq$ Grade 1 and tapered over at least 4 weeks in most cases.

#### **5.4.9. Management of Infusion Reactions**

Subjects in TG E/E1 may experience an infusion reaction associated with administration of study treatment. Signs and symptoms usually develop during or shortly after drug infusion and generally resolve completely within 24 hours of completion of infusion. Nivolumab infusion reactions should be managed according to guidance within the package insert; the treating investigator may use labeled guidance or institutional guidelines for the management of infusion reactions if preferred.

#### **5.4.10. Criteria for Permanent Discontinuation of INCB059872**

The occurrence of unacceptable toxicity not caused by the underlying malignancy will be presumed to be related to study drug treatment and will require that the study drug be permanently discontinued. Unacceptable toxicity is defined as follows:

- Occurrence of an AE that is related to treatment with the study drug that, in the judgment of the investigator or the sponsor's medical monitor, compromises the subject's ability to continue study-specific procedures or is considered to not be in the subject's best interest.
- An AE requiring more than 2 dose reductions.
- Persistent AE requiring a delay of therapy for more than 2 weeks (14 days) unless a greater delay has been approved by the sponsor.

#### **5.4.11. Criteria and Procedures for Dose Increases of INCB059872**

Intrasubject dose escalation will be permitted with sponsor preapproval in the following circumstances:

- The Protocol eligibility criteria are met at the time of escalation.
- The subject has received  $\geq 4$  cycles of study drug without drug-related toxicity  $\geq$  Grade 2.
- The next higher dose level has been determined to be safe based on the MTD criteria.
- The subject is willing to submit to the PK sampling and safety monitoring schedules as in Cycle 1 Day 15.
- In the opinion of the investigator, the subject does not have any concurrent condition or circumstance that would complicate the dose escalation or PK sampling, or pose increased risk to the subject.

## 5.5. Withdrawal of Subjects From Study Treatment

### 5.5.1. Withdrawal Criteria

Subjects **must** be withdrawn from study drug for the following reasons:

- The subject becomes pregnant.
- Consent is withdrawn. Note: Consent withdrawn means that the subject can no longer be followed. Subjects may choose to discontinue study treatment and remain in the study to be followed for disease progression.
- Further participation would be injurious to the subject's health or well-being, in the investigator's medical judgment.
- The study is terminated by the sponsor.
- The study is terminated by the local health authority, IRB, or IEC.
- Unacceptable toxicity has occurred.
- Disease progression has occurred, except in the circumstance where, in the setting of otherwise stable disease, a medical procedure or radiation therapy is required to a single lesion, with medical monitor approval.

A subject **may** be discontinued from study treatment as follows:

- If, during the course of the study, a subject is found not to have met eligibility criteria, the medical monitor, in collaboration with the investigator, will determine whether the subject should be withdrawn from the study.
- If a subject is noncompliant with study procedures or study drug administration in the investigator's opinion, the sponsor should be consulted for instruction on handling the subject.

### 5.5.2. Withdrawal Procedures

In the event that the decision is made to permanently discontinue the study drug, the last date of the last dose of study drug and the reason for subject withdrawal will be recorded in the eCRF. In addition, the following steps should be followed (Note: These visits are described in Section 6):

- The study monitor or sponsor must be notified.
- The reason(s) for withdrawal must be documented in the subject's medical record and in the eCRF.
- The EOT visit should be performed.
- The date of the EOT visit should be recorded in the IRT.
- Subjects must be followed for safety until the time of the follow-up visit or until study drug-related toxicities resolve, return to baseline, are deemed irreversible, or initiation of a new anticancer treatment, whichever occurs first.

If the subject discontinues study treatment and actively withdraws consent for collection of follow-up data (safety follow-up or disease assessment), then no additional data collection should occur; however, subjects will have the option of withdrawing consent for study treatment but continuing in the follow-up period of the study for safety/efficacy assessments.

## **5.6. Concomitant Medications**

All concomitant medications and treatments must be recorded in the eCRF. Any prior medication received up to 28 days before the first dose of study treatment and 30 days after the last dose of study treatment, or until the subject begins a new anticancer therapy, whichever occurs first, will be recorded in the eCRF.

### **5.6.1. Restricted Medications**

- If concomitant administration of an anticoagulant/antiplatelet medication is indicated, caution and enhanced monitoring are required.
  - History of thrombocytopenia and any concurrent INCB059872-related thrombocytopenia should be a factor in the choice of anticoagulant and dose.
- Hydroxyurea is restricted during the treatment periods of the study; however, it may be used to treat hyperleukocytosis per medical monitor approval.

### **5.6.2. Prohibited Medications**

Subjects are prohibited from receiving the following therapies during the screening and treatment periods of this study:

- Use of any anticancer drugs during study.
- Hydroxyurea is prohibited within 48 hours before initiation of study treatment during the screening period and within 24 hours before collection of [REDACTED].
- Aspirin in doses exceeding 81 mg/day.
- Use of potent inhibitors of CYP2D6 or potent inhibitors or inducers of CYP3A4 ([Appendix B](#)).

## **6. STUDY ASSESSMENTS**

All study assessments will be performed as indicated in the schedule of assessments ([Table 7](#)), and all laboratory assessments will be performed as indicated in [Table 8](#). [Table 9](#) presents a summary of clinical laboratory analytes to be assessed. The order of assessments is suggested by the order of mention within the schedule. See Section [7](#) for instructions on each assessment. Further details of study procedures and assessments can be found in the study reference manual.

**Table 7: Schedule of Assessments**

Procedure	Protocol Section	Screening	Treatment						EOT	Follow-Up		Notes
			Cycle 1				Cycles 2+			Safety	Disease Status	
			Days -28 to -1	Day 1	Day 8 (± 2 Days)	Day 15 (± 2 Days)	Day 22 (± 2 Days)	Day 1 (± 2 Day)	Day 15 (± 2 Days)	30 Days (+5 Days)	Every 8-9 Wks	
Informed consent	7.1	X										
Review inclusion and exclusion criteria	3	X	X									
Demography and medical history	7.3	X										
Prior/concomitant medications	7.4	X	X	X	X	X	X	X	X			
Physical examination/ body weight, height	7.5.2	X*	X	X	X	X	X	X	X		* Comprehensive examination at screening, targeted physical examination thereafter. Height at screening only.	
Vital signs	7.5.3	X	X	X	X	X	X	X	X			
12-lead ECG	7.5.4	X	X*	X**	X*				X	X		* Timed triplicate ECG (separated by 2-5 min); predose and 1, 2, and 6 hours postdose. ** Triplicate ECG (separated by 2-5 min) at 1 timepoint approximately 24 hours after last dose.
ECOG status	N/A	X	X	X	X	X	X	X	X			
CT or MRI for solid tumors	7.6, 6.4.2	X						X*		X		X
												* Every 8 weeks (± 7 days) from Cycle 1 Day 1.

**Table 7: Schedule of Assessments (Continued)**

Procedure	Protocol Section	Screening	Treatment						EOT	Follow-Up		Notes	
			Cycle 1				Cycles 2+			Safety	Disease Status		
			Days -28 to -1	Day 1 (± 2 Days)	Day 8 (± 2 Days)	Day 15 (± 2 Days)	Day 22 (± 2 Days)	Day 1 (± 2 Days)	Day 15 (± 2 Days)				
AML/MDS disease assessments	7.6, 6.4.2	X						X*		X		X	* Every 4 weeks from baseline; can be peripheral blood or bone marrow aspirate or biopsy.
MF disease assessments (spleen palpation)	7.6, 6.4.2	X	X					X*		X		X	* Every 4 weeks from Week 4 through Week 24 and every 12 weeks after Week 24.
MF disease assessments (bone marrow assessment)	7.6	X						X*					* Every 24 weeks.
MF subjects: MRI of the upper and lower abdomen and pelvis	7.6	X						X*					* Every 12 weeks from baseline; CT scan may be substituted if MRI is contraindicated.
Review AEs	8.1	X	X	X	X	X	X	X	X	X	X		
Study drug dispensing	N/A		X				X*						* Drug dispensed on Day 1 of each cycle.

**Table 7: Schedule of Assessments (Continued)**

Procedure	Protocol Section	Screening	Treatment						EOT	Follow-Up		Notes
			Cycle 1			Cycles 2+				Safety	Disease Status	
		Days -28 to -1	Day 1	Day 8 (± 2 Days)	Day 15 (± 2 Days)	Day 22 (± 2 Days)	Day 1 (± 2 Day)	Day 15 (± 2 Days)		30 Days (+5 Days)	Every 8-9 Wks	
Administer INCB059872 at site	N/A		X	X*	X*	X*	X**					* Subjects should not take drug at home but must bring medication; they will take their dose after initial PK blood draw. NOTE: Drug is not given on Day 8, but if on a dosing day, subject should follow rules above. ** TG B1 subjects for food-effect study.
Assess compliance	5.3			X	X	X	X	X	X			
Administer ATRA at site			X*	X*	X*	X*						* 45 mg/m  per day administered as 2 evenly divided doses; AM dose only in the clinic.
Administer azacitidine at site			X*	X*	X*	X*	X*					* 75 mg/m  SC or IV for 7 days during the first 9-day or less period (ie, a 2-day break allowed on weekend, if needed) of each 28-day treatment cycle.
Administer nivolumab at site			X*		X*		X*	X*				* 3 mg/kg Q2W.
Distribute reminders	7.10.1	X	X	X	X	X	X	X				

CT = computed tomography; [REDACTED]; MRI = magnetic resonance imaging; [REDACTED]; [REDACTED]

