#### **Reference Therapy, Dosage, and Mode of Administration:**

Conventional regimens of the standard of care combination agents or nivolumab will be used throughout Parts 3 and 4 of the study. Tretinoin capsules (ATRA) will be administered as an open-label commercial product at a starting dose of 45 mg/m^2 per day as 2 evenly divided doses.

Azacitidine will be administered as an open-label commercial product at a starting dose of 75 mg/m^2 subcutaneously or intravenously for 7 days during the first 9-day or less period (ie, a 2-day break allowed on weekend, if needed) of each 28-day treatment cycle.

Nivolumab will be administered at a dose of 3 mg/kg as an intravenous infusion over 60 minutes every 2 weeks.

Premedications should be administered per standard-of-care guidelines.

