#### **1.5. Justification of Route, Dose Regimen, and Treatment Period**

The starting dose of 2 mg INCB059872 administered QOD orally is proposed for this clinical study based on the assessment in GLP toxicology studies.

INCB059872 will be administered orally QOD or QD over a 28-day cycle. Part 1 will be a dose-escalating design in order to determine the recommended dose(s) of INCB059872 for dose-expansion (Part 2).

The proposed starting dose and schedule of INCB059872 for combination therapy is based on preclinical data and emerging clinical data from Part 1 of this study. To ensure safety of INCB059872 in combination with ATRA or azacitidine, the starting dose will be defined as 2 dose levels below the RP2D from Part 1 (monotherapy dose escalation). In Part 3, Treatment Group (TG) C, INCB059872 will be combined with ATRA (tretinoin) based on recent evidence to support synergism between ATRA and LSD1 inhibitors in AML ([Schenk et al 2012](#)). INCB059872 will be administered at a starting dose of 2 mg QD (2 dose levels below the RP2D) in combination with ATRA administered to subjects according to the commercial label ([Vesanoid 2010](#)), a starting dose of 45 mg/m^2 per day administered as 2 evenly divided doses. Treatment Group D will combine INCB059872 at a starting dose of 2 mg QD with azacitidine. The azacitidine regimen selected for use in this study (dose of 75 mg/m^2 SC or IV for 7 days during the first 9-day or less period [ie, a 2-day break allowed on weekend, if needed] of each 28-day treatment cycle) is appropriate to the patient population. The tolerability and activity of this regimen have been established ([Lyons et al 2009](#), [García-Delgado et al 2014](#)) as an acceptable alternative to the recommended dosing schedule of Days 1 to 7 of each 28-day treatment cycle. If tolerated, TG C and TG D will escalate independently and in parallel until the maximum tolerated dose (MTD) or optimal dose(s) of the combination is identified. If the starting dose is not tolerated in any of the combination treatment groups, a lower dose of INCB059872 may be explored; otherwise, higher doses found to be safe and tolerable in Part 1 may be explored.

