### **5.2.2.2. Azacitidine**

In the Parts 3 and 4 TG D and TG D1, azacitidine will be administered in accordance with local prescribing information as an open-label commercial product at a starting dose of 75 mg/m^2 SC or IV for 7 days during the first 9-day or less period (ie a 2-day break allowed on weekend, if needed) of each 28-day treatment cycle. Toxicity associated with azacitidine dosing will be managed per instructions in the package insert ([Vidaza PI 2014](#)).

Investigative sites must provide subjects with administration and storage instructions, as per package insert or institution standard, for azacitidine SC syringes dispensed to subjects for administration away from investigative site.

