#### **4.1.5. Cycle Length and Duration**

Azacitidine will be administered as an open-label commercial product at a starting dose of 75 mg/m^2 subcutaneously or intravenously for 7 days during the first 9-day or less period (ie, a 2-day break allowed on weekend, if needed) of each 28-day treatment cycle. Nivolumab will be administered at a dose of 3 mg/kg as an intravenous infusion over 60 minutes every 2 weeks (Day 1 and Day 15 of each 28-day treatment cycle).

For combination therapy (Parts 3 and 4), Cycle 1 Day 1 is the day that the first dose of INCB059872, ATRA, azacitidine, or nivolumab is administered. Actual Day 1 of subsequent cycles will correspond with the first day of administration of azacitidine or nivolumab in that cycle; thus, treatment cycles may become out of sync with the originally planned schedule and cycle length may be different from 28 days. The date of Day 1 of subsequent cycles recorded on the eCRF will be used as Day 1 of the subsequent cycles.

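### Table 7 marks azacitidine at the Cycle 1 Day 15 and Day 22 visits, neither of which can be a dosing day under the regimen in the row's own note and in the rest of the text

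*Protocol*

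**What the plan says.** Protocol Section 6 makes Table 7 the schedule by which study assessments are carried out, and Section 6.2 ties visit dates to the windows in that table. The azacitidine row, "Administer azacitidine at site", has five marks: Cycle 1 Day 1, Day 8, Day 15 and Day 22, and Day 1 of Cycles 2+. The Cycles 2+ Day 15 cell is empty. Each mark carries an asterisk, and the note for it specifies 75 mg/m² "for 7 days during the first 9-day or less period (ie, a 2-day break allowed on weekend, if needed) of each 28-day treatment cycle".

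The regimen is stated in four other places, always in the same terms:

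- Protocol synopsis, reference therapy: "subcutaneously or intravenously for 7 days during the first 9-day or less period (ie, a 2-day break allowed on weekend, if needed".
- Protocol Section 1.5: "SC or IV for 7 days during the first 9-day or less period [ie, a 2-day break allowed on weekend, if needed". It is presented there as an accepted alternative to dosing on Days 1 to 7.
- Protocol Section 5.2.2.2: "SC or IV for 7 days during the first 9-day or less period".
- SAP Section 4.1.5: "subcutaneously or intravenously for 7 days during the first 9-day or less period".

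Protocol Sections 4.1.3 and 5.4.3 set the DLT period for the combination dose-finding groups as the whole of Cycle 1, through Day 28.

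**The concern.** Azacitidine is given only in Treatment Groups D and D1. In Group D, Cycle 1 is the period on which escalation decisions rest. Section 1.6.4 names myelosuppression as the main dose-limiting toxicity of azacitidine, and Table 4 counts defined hematologic events as DLTs. Section 4.1.3 also intends the doses of the combination agents to stay the same across dose-finding and expansion cohorts. It should therefore be unambiguous which days in Cycle 1 are azacitidine days.

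The row as printed leaves that open. Two of its marks sit at visits that its own note excludes. A site that acted on the marks and a site that acted on the note would give different amounts of azacitidine in the same DLT window, and the DLT count, the cytopenias and the azacitidine exposure would then not all describe one regimen.

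**Working it through.** The plan gives no figure to reproduce here. The check is whether the marked visits can coincide with the stated dosing days.

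**1. Are the marks in the columns claimed?** Two neighbouring rows on the same page of Table 7 serve as controls.

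- Nivolumab, given every 2 weeks, is marked at Cycle 1 Days 1 and 15 and at Cycles 2+ Days 1 and 15. That is where a two-weekly drug should fall.
- INCB059872 has the same five-cell pattern as azacitidine. Its fifth mark, for the food-effect study, lands on Cycles 2+ Day 1. Sections 5 and 7.8.4 place the food-effect dose on Cycle 2 Day 1.

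Both rows support reading the azacitidine marks as Cycle 1 Days 1, 8, 15 and 22 and Cycles 2+ Day 1.

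**2. Can each Cycle 1 visit be a dosing day?** The regimen allows dosing only within Days 1 to 9. The visit windows come from the Table 7 headers.

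| Cycle 1 visit | Permitted dates | Days shared with Days 1 to 9 |
|---|---|---|
| Day 1 | Day 1 | 1 |
| Day 8 ±2 | Days 6 to 10 | 4 (Days 6 to 9) |
| Day 15 ±2 | Days 13 to 17 | 0 |
| Day 22 ±2 | Days 20 to 24 | 0 |

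The Day 1 and Day 8 marks are compatible with the text. The Day 15 and Day 22 marks are not, on any permitted date.

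**3. Does the grid agree with itself?** A Day 15 visit exists in Cycle 1 and in later cycles. Azacitidine is marked at the first and not at the second, under one note that covers every cycle. No section describes a different azacitidine schedule for Cycle 1.

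**4. What range of exposure is possible?**

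- Note followed: 7 × 75 = 525 mg/m² in Cycle 1, a difference of 0%.
- One dose at each of the two visits in addition to the full course: (7 + 2) × 75 = 675 mg/m². The ratio is 675/525 = 1.286, or +29%.

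**The case against.** The strongest reply is that the marks are conditional. Each carries the asterisk that leads to the 7-days-in-9 limit in the same row, so a site meets the limit as it reads the mark. The table uses notes this way elsewhere: the INCB059872 row marks Day 8 and then notes that drug is not given that day unless it is a dosing day. Nor can the grid serve as an azacitidine calendar, since it has no columns for Days 2 to 7. The ATRA row likewise marks only four Cycle 1 visits for a drug given daily. Any departure would also leave a trace: SAP Section 6.4.3 summarises azacitidine dose intensity against an assigned dose built on seven doses per 28-day cycle, and SAP Section 6.3 summarises protocol deviations.

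Most of this stands, and it limits the consequence. It does not remove the contradiction. The Day 8 note for INCB059872 tells the site what to do at the marked visit; the azacitidine note gives no meaning to a mark at Day 15 or Day 22. The dose-intensity and deviation summaries would describe a departure afterwards, not prevent it.

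Two stronger readings are tempting and are not supported:

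- A reader might infer that Group D subjects will receive 29% more azacitidine in Cycle 1, or that its DLT data will be distorted. The 29% is the top of a range that starts at zero, and it requires a site to act against the note on the very marks it is following.
- A reader might infer that Cycle 1 and later cycles ought to be marked identically. Cycles 2+ have no Day 8 or Day 22 column, so marks at Day 1 and Day 8 in Cycle 1 and at Day 1 alone afterwards are what a single regimen would produce on this grid. Only the difference at Day 15 is an inconsistency.

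**Conclusion.** The inconsistency is real and confined to one row. The Cycle 1 Day 15 and Day 22 azacitidine marks cannot be reconciled with the row's note, the synopsis, Protocol Sections 1.5 and 5.2.2.2, or SAP Section 4.1.5. It concerns Groups D and D1 only. It matters chiefly because both marks fall in the DLT window for Group D.

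Its possible effect on Cycle 1 azacitidine runs from none to two added administrations (675 against 525 mg/m², +29%). The upper end assumes a complete 7-day course, one further dose of 75 mg/m² at each of the two visits, and disregard of the note. The conclusion also rests on the column positions; the nivolumab and INCB059872 rows bear these out, and they can be confirmed on the typeset page. No endpoint definition, analysis population or futility rule is affected. It is a modest point, but worth correcting because the row concerns drug administration during DLT assessment.

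**What to change.** Reconcile the azacitidine marks in Table 7 with the note in the same row and with the regimen statements in the synopsis, Protocol Sections 1.5 and 5.2.2.2, and SAP Section 4.1.5, so that all of them describe the same dosing days. Which of them is right is for the sponsor to decide, and this review takes no position on it. If the Day 15 and Day 22 marks are meant to record something other than administration, the row should say so.

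A clarification letter to sites, or an entry in the next amendment, is enough. If the marks alone change, the cost is the correction of one table row. No sample size or analysis is affected by such a correction.
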